## 7. Study Visit Procedures

### 7.1 Pre-screening

Prior to start of the study, prospective subjects will be screened for eligibility requirements by telephone. Subjects who are interested will then be scheduled for a screening visit. Additionally, if subjects express an interest in the procedure during a clinic appointment with [name], he may discuss the study with them and assess the treatment area. If a subject is still interested and deemed a good candidate, the PI will connect the patient with a research coordinator to answer any further questions and provide consent for review.

### 7.2 Screening Visit (Visit 1)

The purpose of the study and specific inclusion and exclusion criteria and potential risks will be discussed with the potential study subject. All interested subjects will be given the Informed Consent Form with adequate time for review. The Investigator and/or designee will address questions and concerns raised by the subject. Those subjects who elect to participate, will sign the Consent Forms prior to any study procedures.

Subjects will be screened to ensure that they meet all study criteria. The following enrollment and screening activities will be performed:

- a. Discuss the bipolar fractional radiofrequency device with each subject presenting for treatment
- b. Obtain informed consent and HIPAA authorization
- c. Collect any appropriate medical and surgical history including current medications, skin type, recent sun exposure, allergies, major illnesses, etc.
- d. Close-Up and standard photography
- e. Surface area assessments via the Vectra H2 3D Imaging System and Standup Vectra
- f. Images will be obtained using the optical coherence tomography, BTC 2000, Bio Aquaflux, and/or high-resolution ultrasound.
- g. Urine pregnancy test for women of childbearing potential
- h. Examination of the treatment area by the physician
- i. Location and approximate area of treatment area (s) will be mapped
- j. Pre-existing skin conditions will be evaluated for potential study impact
- k. Other assessments may be conducted per the clinical sites standard practice
- l. Weight measurement

This visit will take about 1.5 – 2.5 hours

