### 7.3 Treatment Visit (Visit 2)

The treatment visit activities may be combined with the Screening Visit. Prior to treatment, the treatment area should be cleaned of all debris cosmetics with antiseptic cleanser. Subjects may be given subcutaneous injection with 0.5%-1.0% lidocaine with epinephrine 1:100,000 -200,000 (or carbacaine 3% for those who intolerant of epinephrine) to anesthetize the areas and for hemostasis control. Starting with lower volumes of injectable anesthetic and increased as needed to achieve effective pain and hemostasis control. Total injected volume to treatment area should not exceed 50cc and must be in consideration of safe weight-based dosage limits of medications with systemic and local toxic effects. During administration of local injectable anesthetic, provider prescribed chilled air, topical anesthetic, inhaled analgesia, and/or oral sedative may be prescribed for additional palliative measures.

The following activities will be performed on all subjects:

- a. The study treatment (bipolar fractional radiofrequency) per study treatment guidelines provided
- b. Review of post treatment expectation and management for the treatment as detailed in the study device instruction for use (IFU)
- c. All expected (e.g., edema, erythema) and unexpected (e.g., burn, blister) treatment adverse events will be documented and graded
- d. During the treatment, subjects will be asked to rate any pain or discomfort using an eleven-point Numerical Pain Rating Scale (NPRS)

The following activities will also be for exploratory purposes:

- a. Collection of two 0.33mm biopsies using WellTech Rapid-Core 0.33mm Biopsy Punch pre-treatment. The biopsy will be taken from the submental skin within the designated area for treatment. One biopsy will be used for histological studies and the other for gene expression studies

This visit will take about 2-3 hours.

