## 8. Schedule of Events

Procedures	Pre-Screening	Screening: Visit 1 #	Treatment: Visit 2 (Day 0) #	Follow Up: Visit 3 (Month 3)	Follow Up: Visit 4 (Month 6)
Telephone/Telehealth Screen	X				
Informed Consent		X			
Inclusion/Exclusion Criteria		X			
Demographics		X			

Medical History/Concomitant Medications		X	X	X	X
Physical Exam		X			
Urine Pregnancy		X			
Treatment			X		
Standard Photographs		X		X	X
Surface area assessment using the H2 3D Imaging System and Standup Vectra		X		X	X
Clinician GAIS					X
Non-invasive Skin Tests*		X		X	X
Biopsy			X	X	X
Safety Assessment			X	X	X

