## 16. Subject Safety and Data Monitoring

For this protocol, which involves the use of a non-significant risk device, the Investigator will be responsible for the conduct of the study including accrual, subject experience, attrition, patterns of expected adverse events and/or unexpected adverse events, any protocol deviations or violations, and any changes in the risk/benefit analysis.

Subjects will be asked about any adverse events throughout the study by the study staff. Subjects will be asked to contact the study staff if adverse events develop between visits. An unscheduled visit will be arranged so that the Investigator can clinically evaluate and photograph these findings. All subjects will be discontinued from the study if their problem remains unchanged/becomes worse. The Investigator can decide to stop the study if he/she believes that the participants' participation is no longer safe or if another treatment may be more helpful. The IRB or FDA may stop the research for the safety of the participants. These adverse events will be documented and reported as required for compliance with applicable regulations.

All study records and information will be identified by the subject number. All subject identifiers will be removed from all documents. The link between subject name and study ID number will be kept in separate password-protected files at the study site. Documents containing identifying information will be kept in locked files in the research staff's locked office. All electronic study data will be password protected with access limited to members of the research team. No direct identifying information will be shared with any outside entities, unless required by regulatory agencies (FDA and IRB). Electronic data (electronic data entry - Case Report Forms) if used will be password protected.

Photographs of the subject's face will be taken at Enrollment/Treatment and Follow-Up visits. These photographs will be identified by subject numbers. Subject confidentiality will be protected to the greatest extent possible. Quantitative surface area assessments will be done on lateral 3D images taken at baseline and compared with 3D images obtained at all follow-up visits.

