## 18. Sources of Research Material

Demographics and medical history will include age, gender, weight, height, BMI, skin type, recent sun exposure, allergies, current medications, major illnesses, photographs, adverse events and treatment. Additionally, OCT images, ultrasound images, TEWL measurements, BTC 2000 measurements, and biopsies will be obtained.

High resolution ultrasound will be used to assess skin thickness and density. The standard time for use of high-resolution ultrasound should take approximately 5 minutes.

Transepidermal water loss (TEWL) measurements will be used to evaluate barrier function of the skin epidermal layer to determine progress of epidermal healing after treatment. The standard time for TEWL measurements should take approximately 5 minutes. Optical coherence tomography (OCT) will be used to noninvasively gather topographical and histologic images of pre- and post-treated skin. The standard time for OCT should take approximately 5-10 minutes. The BTC 2000 will be used to measure skin laxity, viscoelastic deformation, stiffness, energy absorption, elasticity, and deformation values of skin. The standard time for BTC 2000 should take approximately 5 minutes.

[figure not shown]
Biopsies will be taken using 0.33mm biopsy punches of the submental area. Biopsies will allow investigators to correlate changes seen in skin measurements with histology and gene expression. Time for two biopsies will take approximately five minutes. Biopsies for histology will be fixed immediately after collection in 4% PFA followed by paraffin embedding. Biopsies for gene expression will be put in RNA-Later solution and transferred to the Plastic Surgery Research Lab for gene expression analysis. Whole genome sequencing will not be performed, we will only be analyzing proteins and RNA expression related to collagen, elastin, and the extracellular matrix production.

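### Baseline 3D scans, photographs and skin tests are tied to Screening with no limit on the gap to treatment, so when visits are split the change from baseline includes an untreated interval of unspecified length

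*Combined protocol and SAP*

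**What the plan says.** Section 7.2 lists the baseline outcome measurements among the Visit 1 activities: item (d), "Close-Up and standard photography"; item (e), "Surface area assessments via the Vectra H2 3D Imaging System and Standup Vectra"; and item (f), "Images will be obtained using the optical coherence tomography, BTC 2000, Bio Aquaflux, and/or high-resolution ultrasound". Weight is item (l) of the same list.

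The Schedule of Events (Section 8) agrees. The row "Surface area assessment using the H2 3D Imaging System and Standup Vectra" is marked at Screening, Month 3 and Month 6, and so are the rows for standard photographs and non-invasive skin tests. All three are blank in the Day 0 column.

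Section 7.3, on the treatment visit, lists no scan, photograph or skin test. The one tissue or imaging outcome it fixes before treatment is the biopsy: "Collection of two 0.33mm biopsies using WellTech Rapid-Core 0.33mm Biopsy Punch pre-treatment". The same section says "The treatment visit activities may be combined with the Screening Visit", and a footnote to the Schedule repeats this as an option.

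Section 7.4 times follow-up at 3 and 6 months after treatment, each within 7 days. Section 9 defines change as the post-baseline value minus the baseline value, without saying which visit supplies baseline. The nearest definition, in Section 6.2, equates baseline with pre-procedure and gives no time limit. Section 16 says "Photographs of the subject's face will be taken at Enrollment/Treatment and Follow-Up visits".

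**The concern.** The later end of each before/after comparison is held to within a week, counted from treatment. The earlier end is not tied to treatment at all. A subject screened and treated on one day and a subject screened well before treatment both contribute a change from baseline, but the second subject's change includes a period in which nothing had been done.

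Section 3 describes a non-controlled study of up to 15 subjects, so no comparison group can show or remove what happened in that period. Anything that shifts submental contour or skin readings between Screening and Day 0, such as weight, sun exposure, season or topical products, enters the primary percent change. It also enters the photograph pairs of Section 10, where improvement means that at least two of three raters pick out the post-treatment image. Sections 4 and 5.1(h) restrict other dermatological and aesthetic procedures, which covers only some of these influences.

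A smaller matter concerns the biopsies. Section 18 states the aim "Biopsies will allow investigators to correlate changes seen in skin measurements with histology and gene expression". With split visits the biopsy baseline is Day 0 and the skin-measurement baseline is an earlier day, so the two changes to be correlated cover different intervals.

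**Working it through.** The plan gives no figure on this point, so there is nothing to reproduce. The check sets the timing provisions side by side and then works out how much calendar time an assumed gap would add.

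**1. Where each baseline is taken (Section 8, consistent with 7.2 and 7.3)**

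| Measurement | Screening | Day 0 | Month 3 | Month 6 |
|---|---|---|---|---|
| 3D surface scans | X | – | X | X |
| Standard photographs | X | – | X | X |
| Non-invasive skin tests | X | – | X | X |
| Biopsy | – | X | X | X |

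**2. The gap G between Visit 1 and Visit 2.** Its lower end is 0, because Section 7.3 and the Schedule footnote allow one combined visit. It has no stated upper end, and no section requires a repeat of the scans, photographs or tests when treatment comes later.

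**3. What the Section 9 difference contains.** Write Y(S) for the value at Screening, Y(0) for the unmeasured value just before treatment and Y(6) for the Month 6 value. Then

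Y(6) − Y(S) = [Y(6) − Y(0)] + [Y(0) − Y(S)].

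Only the first bracket can contain a device effect. The second is pre-treatment change. With split visits Y(0) is not scheduled for any of the first three rows above, so the brackets cannot be separated afterwards. With combined visits S and 0 are the same day and the second bracket vanishes.

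**4. Calendar time under an assumed gap.** G is an assumption; the documents give none. Months are taken as 30 days. Baseline-to-Month-6 span = G + 180 ± 7 days. Untreated share of time = G/(G + 180) for Month 6 and G/(G + 90) for Month 3.

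| Assumed G | Span to Month 6 | Untreated share, Month 6 | Untreated share, Month 3 |
|---|---|---|---|
| 0 days | 173–187 days | 0% | 0% |
| 30 days | 203–217 days | 30/210 = 14% | 30/120 = 25% |
| 90 days | 263–277 days | 90/270 = 33% | 90/180 = 50% |

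Turning these into bias would need a rate of drift for each measurement without treatment. The documents give none, so neither the size nor the direction of [Y(0) − Y(S)] can be computed.

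**The case against.** The strongest reply is that the gap may be short or nil in practice. Section 4 recruits people who already present for this treatment, and a combined visit is allowed. Nothing in the documents points to gaps of months. This is fair, and it limits the likely size. It does not close the point, because combining visits is a permission and the protocol neither bounds the gap nor asks for it to be reported.

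A second reply is that the larger weakness is the missing control group. Weight, season and sun exposure also vary over the six months after treatment, and a Day 0 baseline leaves that untouched. This stands. Background change after Day 0 is a limit of a single-arm study, and Section 1 calls the evaluation exploratory. The pre-treatment portion differs in that it can be avoided by rescheduling.

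A third reply is that the biopsy mismatch is minor: biopsies are exploratory, only for consenting subjects, and Section 9 specifies no correlation analysis. That also stands, and the mismatch is secondary here.

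A fourth is that a maximum gap, with repeat imaging only when it is exceeded, would be lighter. It would bound the problem. Measuring before treatment on Day 0 removes it.

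Three stronger readings are tempting and not supported:

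- A reader might take 14% to 33% as the fraction of the observed effect that is spurious. It is a share of calendar time under an assumed gap.
- A reader might infer that follow-up length differs between subjects. Time from treatment to follow-up is the same for all, within the 7-day windows of Section 7.4. Only the span from baseline varies.
- A reader might see Section 16 as contradicting the Schedule. Its label can mean either visit or the combined visit, and Section 7.2 itself describes Visit 1 activities as enrollment. The sentence concerns face photographs only. It is ambiguous and needs clarifying, but it is not a clear conflict.

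**Conclusion.** The point holds as a gap in the baseline definition that reaches the primary efficacy endpoint. Following the Schedule as written, any subject with separate Visits 1 and 2 has an untreated interval of unspecified length inside the change from baseline for the 3D scans, the blinded photograph pairs and the instrument measures. The design offers no means of separating it out.

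The effect is zero for subjects treated on the day of screening. For others it is unknown in size and sign, and the calendar shares above rest wholly on the assumed 1 to 3 months. If most subjects have combined visits, the practical effect will be small, but the protocol does not ensure this. Once a subject has been treated without Day 0 measurements, the omission cannot be repaired. This is a cheap improvement worth making before enrollment, not a flaw that invalidates the study.

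**What to change.** - In Sections 6 and 9, define baseline as the last measurement before treatment.
- In Sections 7.2 and 7.3, state that when the visits fall on separate days, items 7.2(d) to (f) are performed at Visit 2, before anesthetic injection, biopsy and treatment. Take weight (7.2(l)) then as well, so that it belongs to the same day as the imaging baseline. The Screening weight may still be needed to confirm the BMI criterion in 5.1(c).
- Change the Schedule cells to match, and state in Section 16 which visit its enrollment/treatment label means.

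The scans, photographs and skin tests are moved, not added; the only possible addition is a second weighing. No criterion in Section 5 depends on these instruments, since submental fat is graded by the investigator, so screening loses no information. The downside is a longer Visit 2, already stated at 2 to 3 hours, and a shorter Visit 1 for subjects with split visits. As a guide to the added time, the follow-up visits in Section 7.4 include the same scans, photographs and tests along with an examination and biopsies, and are put at 45 minutes to 1 hour in total.

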### 7.3 Treatment Visit (Visit 2)

The treatment visit activities may be combined with the Screening Visit. Prior to treatment, the treatment area should be cleaned of all debris cosmetics with antiseptic cleanser. Subjects may be given subcutaneous injection with 0.5%-1.0% lidocaine with epinephrine 1:100,000 -200,000 (or carbacaine 3% for those who intolerant of epinephrine) to anesthetize the areas and for hemostasis control. Starting with lower volumes of injectable anesthetic and increased as needed to achieve effective pain and hemostasis control. Total injected volume to treatment area should not exceed 50cc and must be in consideration of safe weight-based dosage limits of medications with systemic and local toxic effects. During administration of local injectable anesthetic, provider prescribed chilled air, topical anesthetic, inhaled analgesia, and/or oral sedative may be prescribed for additional palliative measures.

The following activities will be performed on all subjects:

- a. The study treatment (bipolar fractional radiofrequency) per study treatment guidelines provided
- b. Review of post treatment expectation and management for the treatment as detailed in the study device instruction for use (IFU)
- c. All expected (e.g., edema, erythema) and unexpected (e.g., burn, blister) treatment adverse events will be documented and graded
- d. During the treatment, subjects will be asked to rate any pain or discomfort using an eleven-point Numerical Pain Rating Scale (NPRS)

The following activities will also be for exploratory purposes:

- a. Collection of two 0.33mm biopsies using WellTech Rapid-Core 0.33mm Biopsy Punch pre-treatment. The biopsy will be taken from the submental skin within the designated area for treatment. One biopsy will be used for histological studies and the other for gene expression studies

This visit will take about 2-3 hours.

#### *Post-treatment care and precautions*

Appropriate post-treatment care instructions will be provided as deemed appropriate by the Investigator or study staff.

Post treatment assessment will be performed. Subjects will be instructed that blistering, bleeding, oozing, strong pain, swelling persisting for more than 72 hours, or signs of infection (e.g., pus, drainage, fever) are cause for immediate concern and they should contact the investigator and/or his designee, to be evaluated. Downtime after treatment typically can last approximately 0-2 days.

#### 7.4 Follow-up Visits (Visits 3 and 4)

At a minimum, all subjects will return for follow-up at 3 months (+/- 7 days) and 6 months (+/- 7 days) after treatment.

The following activities will be performed on all subjects during the follow-up visits:

- a) The physician or study staff will perform an examination of the skin of the treatment area.
  - All expected (e.g., edema, erythema) and unexpected (e.g., burn, blister) treatment local skin responses will be documented and graded at every visit
- b) Adverse Event Review
  - Query the subject regarding any change in health since enrollment into the study.

- Perform a detailed cutaneous exam of the treatment area, review and record any local adverse events related to cutaneous changes.

c) Collect an updated surgical history and record any change in concomitant medications or treatments.

d) Images will be obtained using the optical coherence tomography, BTC 2000, Bio Aquaflux, and/or high-resolution ultrasound, as was done previously.

e) The two small biopsies within the treatment area will be taken at each visit.

f) Take close-up and standard photography

g) Surface area assessments via the Vectra H2 3D Imaging System and Standup Vectra

These visits will take about 45 minutes – 1 hour.

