### 6.1.2 Primary Safety Endpoint

- Incidence, severity, and relatedness of adverse events

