### **Safety Endpoint**

Safety will be determined based on adverse event data collected from both the Profound treatment visit and all follow-up evaluations of the treated areas. The Primary Safety Endpoint will be the incidence rate, severity, and relatedness of the adverse events that are observed in the study. All adverse events that arise during the course of the study will be recorded and summarized in the final study report.

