#### ***Bruising: (Rare)***

A mild bruising may occur at the treatment area as a result of radiofrequency exposure. This is usually transient and resolves in a few hours to few days.

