#### ***Transient edema and/or erythema: (Occasionally)***

May develop within the irradiated areas but are usually temporary and fade within 24-72 hours.

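### No safety contact is scheduled between the treatment day and Month 3, so mild or delayed transient events may be under-recorded in the primary safety endpoint

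*Combined protocol and SAP*

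**What the plan says.** The primary safety endpoint (Section 6.1.2) is "Incidence, severity, and relatedness of adverse events". The Safety Endpoint text in Section 6 gives its source: "Safety will be determined based on adverse event data collected from both the Profound treatment visit and all follow-up evaluations of the treated areas".

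Section 7.4 sets the follow-up, as a minimum: "all subjects will return for follow-up at 3 months (+/- 7 days) and 6 months (+/- 7 days) after treatment". In Section 8 the Safety Assessment row is marked at Day 0, Month 3 and Month 6. The table has no visit, call or diary between the first two.

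Section 13 describes edema and erythema as "usually temporary and fade within 24-72 hours". On bruising it says: "This is usually transient and resolves in a few hours to few days".

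The protocol has other capture routes:
- Section 7.3 has treatment adverse events documented and graded at the treatment visit, and its post-treatment text adds an assessment after the procedure.
- The same post-treatment text lists signs for which subjects should contact the investigator: blistering, bleeding, oozing, strong pain, signs of infection, and swelling that lasts beyond 72 hours.
- Section 16 asks subjects, with no severity threshold, to contact staff if adverse events develop between visits.
- Section 7.5 schedules an event visit within 24 hours of a report, with history, examination and photographs, and an adverse event form if the event qualifies.
- Section 7.4 has staff ask at each follow-up visit about changes in health since enrollment.
- Section 15.2 collects events from consent to study exit.

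**The concern.** The events that the protocol itself describes as short-lived should be over long before the next scheduled look. For anything mild that begins, or reaches its worst, after the subject goes home on Day 0, the study depends on one of two things: the subject choosing to call, or the subject remembering it at Month 3.

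Safety is a primary endpoint here, so incomplete capture affects a main result. The study extends the device to submental tissue and enrolls Fitzpatrick types I-VI (Section 5.1), while Section 12 describes the clearance for types I-III. Early tolerability in this setting is therefore part of what the study is meant to learn. Events that go unrecorded lower the reported incidence. For events that are recorded late, the grade and duration rest on recollection.

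**Working it through.** The plan states no expected adverse-event rate, capture rate or precision target for safety, so it has no figure to reproduce. The checks below use the visit timing and N = 15 (Section 3 says up to 15).

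**1. The gap in days.** Take 3 months as 90 or 91 days, with the window of 7 days either side.
- 90 days: day 83 to 97. Subtracting the 3 days (72 hours) stated for edema and erythema leaves 80 to 94 days.
- 91 days: day 84 to 98. Subtracting 3 leaves 81 to 95 days.

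If edema and erythema behave as Section 13 says, the next scheduled assessment comes about 80 to 95 days after they have gone.

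**2. What each route can see in that gap.**
- Treatment-day grading sees what appears before the subject leaves a visit of about 2-3 hours. It cannot record later onset, a later peak or the date of resolution.
- The call list omits bruising, erythema, crusting and swelling under 72 hours. Its swelling threshold equals the upper end of Section 13's expected duration, so swelling that runs the expected course is not on it.
- The Section 16 request covers any adverse event but still needs the subject to act.
- The Month 3 question looks back about three months.
- Water-loss measurement, which Sections 13 and 18 say is meant to follow epidermal healing, is scheduled after treatment only at Months 3 and 6, so no early instrument reading fills the gap.

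**3. How incomplete capture would act.** Let p be the true share of subjects with a given event that Day 0 grading does not see, and c the share of those events that is recorded. Both are assumptions; the documents give neither. Recorded rate = p × c, and P(at least one recorded) = 1 − (1 − p × c)^15.

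| True rate p | c = 100% | c = 75% | c = 50% | c = 25% |
|---|---|---|---|---|
| 5% | 0.537 | 0.436 | 0.316 | 0.172 |
| 10% | 0.794 | 0.689 | 0.537 | 0.316 |
| 20% | 0.965 | 0.913 | 0.794 | 0.537 |

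At p = 20%, the expected counts in 15 subjects are 3.0, 2.25, 1.5 and 0.75, and the recorded rates are 20%, 15%, 10% and 5%. One missed subject is 1/15 = 6.7 percentage points.

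**4. Reading a zero.** If no subject has a given event recorded, the one-sided 95% upper limit is 1 − 0.05^(1/15) = 18.1% (two-sided: 1 − 0.025^(1/15) = 21.8%). This limit applies to p × c. With c = 50%, again an assumption, the one-sided limit on p itself is 18.1% / 0.5 = 36.2%.

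**5. What is least affected.** A subject already counted on Day 0 for erythema stays counted in an overall any-event rate. The possible loss is mainly in rates by event type, in peak grade and in duration.

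**The case against.** The strongest reply is that the protocol has several capture routes. Immediate reactions are graded on Day 0. Section 16 invites reports of any adverse event, not only alarming ones, and Section 7.5 turns a report into an examination within 24 hours. Blistering and swelling beyond 72 hours are on the call list. Scarring and persistent pigmentary change can be seen at the Month 3 and 6 skin examinations. Section 13 labels bruising and blistering or crusting as rare and gives no onset times. Section 7.4 sets its visits as a minimum. The study is small, single-arm and exploratory, with a cleared device.

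Most of this stands, and it rules out some tempting readings. A reader might infer that the primary safety endpoint rests on three-month recall. It does not, because of Day 0 grading and the reporting routes in Sections 7.5 and 16. A reader might also infer that the instruction in Section 7.4 to grade local skin responses at every visit contradicts the schedule. It does not, because persistent or late responses can be graded at Months 3 and 6.

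The reply does not remove the gap. A minimum permits extra contacts but requires none. An open request to call is still passive, and the more specific instruction given after treatment leaves out the mild transient events.

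**Conclusion.** The point holds in a limited form. Between Day 0 and Month 3, adverse-event capture is subject-initiated, backed only by a retrospective question at Month 3. Mild or delayed-onset transient events, together with their peak severity and duration, may be under-recorded in the primary safety endpoint. Longer-lasting events, blistering and prolonged swelling are better covered.

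The timing gap of about 80 to 95 days follows from the protocol's own figures, provided these events run the course that Section 13 describes. A reader might go further and state that the reported incidence is biased low by a definite amount. The documents do not support that: missed events can only lower a count, but no capture rate or true incidence is given, and part of the reactions is seen on Day 0. The table above illustrates the mechanism and is not an estimate. This is an inexpensive improvement worth making; it does not invalidate the safety assessment.

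**What to change.** Add to Section 7.4, and as one column in Section 8, a single scripted adverse-event query by telephone or electronic form for every subject. The investigators set its time within the window that Section 13 gives for these events. Record onset, grade and resolution date for each event. State in the Safety Endpoint text that these data count toward the primary safety incidence alongside the visit data. For an event still present at the query, complete the resolution date from a later contact or visit.

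This is data collection only; treatment and post-treatment care stay as written. The cost is one short contact for each of at most 15 subjects, and the study already screens by telephone (Section 7.1). Events disclosed in the query may lead to additional event visits under the existing Section 7.5, so the protocol should say how the two connect. The reported adverse-event rate will probably be higher.
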